9.5 Unblinding details (Treatment Received)

After a patient is randomized, IXRS assigns a kit to that patient. Each kit is split into several boxes (one for Week 1, one for Week 2, one for Week 3, one for Week 4 to 7 and one for Week 8 to 11). Each box comprises several bottles of the study drug.

At each visit (Baseline, Visit 3 and Visit 4), the site entered the bottle number (barcode) and the number of tablets in the bottle that was dispensed (and returned). In the event, that the bottle number was not available, the site has been instructed to enter key information (kit ID, week number and type of bottle) to allow the unblinding instead of the bottle number. The kit ID from the integration with

The first step for the unblinding (to determine which treatment received) will be to link the bottle number (when available) with the kit ID using the packaging kit list. In instances where the bottle number is not available (not a numeric value), the kit ID recorded as part of the bottle number information will be used to determine the Kit ID. Once each record from the drug accountability CRF page has been linked to the actual kit ID, the kit list from IXRS will be used to determine the treatment group (low dose pitolisant, high dose pitolisant or placebo).

The actual treatment group for the analysis will be derived as detailed in Section 10.2.

9.6 Double-Blind and OLE Analyses Reporting

The data collected for the Double-Blind Treatment Phase and the OLE Phase are included in the same database.

A CSR will be written at the end of the Double-Blind Treatment Phase and another one at the end of the OLE Phase. The date of first dose in the OLE Phase will be used to determine if the patient entered the OLE Phase.

Double-Blind Treatment Phase:

For reporting of the Double-Blind Treatment Phase analyses, a data cut-off will be applied to the datasets and only data related to the Double-Blind Treatment Phase will be reported, i.e.,

- Baseline and baseline characteristics
- Visits performed in the Double-Blind Treatment Phase, up to and including Visit 5 (Week 11) for patients who entered the OLE Phase and through the safety follow-up visits for patients who opt out of the OLE Phase
- For patients who entered the OLE Phase, any AE or medication that started up to and excluding the first dose of study drug in the OLE Phase.
- For patients who opt out of the OLE Phase, all AEs and medications reported through the final 30-day safety follow-up telephone contact will be reported as part of the Double-Blind Treatment Phase

The date of first dose in the OLE Phase will be kept in the datasets to determine if the patient has entered the OLE Phase.

OLE Phase:

For reporting of the OLE analyses, no data cut-off will be applied to the datasets but only data related to the OLE Phase will be reported, i.e.,

- Demographics and baseline characteristics for patients who received at least one dose of study drug within the OLE Phase
- Baseline of the safety and efficacy data (section 9.3)
- Safety and effectiveness reported during the OLE Phase
- AE and concomitant medications started on or after the 1st dose of OLE study drug intake

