12.6.1 Adverse Events

An AE is defined as any untoward medical occurrence associated with the use of a drug in humans, whether or not considered drug related.

A TEAE is defined as any event not present before exposure to study drug or any event already present that worsens in intensity or frequency after exposure and up to 30 days after the last dose of study drug. For the OLE Phase, any AE starting on or after the first dose of OLE treatment will be considered treatment emergent.

A serious AE (SAE) is defined as any AE that results in any of the following outcomes: death, is life-threatening, results in inpatient hospitalization or prolongation of existing hospitalization, results in a persistent or significant incapacity or substantial disruption of the ability to conduct normal activities of daily living, or is a congenital anomaly/birth defect. Important medical events that may not result in death, be life-threatening, or require hospitalization may be considered SAEs when, based upon appropriate medical judgment, they may jeopardize the patient and may require medical or surgical intervention to prevent one of the outcomes listed in this definition.

The AE's relationship to study treatment will be evaluated by the investigator. The following relationships will be collected in eCRF: definitely related, probably related, possibly related,

unlikely related, or not related. The AEs that are evaluated as definitely, probably, or possibly related (or with missing relationship) will be considered treatment-related AEs for summary purposes.

The severity of AEs will be classified by the investigator as mild, moderate, or severe. If the severity is missing, the AE will be assumed to be severe.

An overall AE summary will be generated presenting the frequency and percentage of patients and the number of AEs for the following categories. This overall summary will also be provided for each age groups (6 to <12 years; 12 to <18 years and 18 years or older) for the Double-Blind Treatment Phase. The same summary may be repeated for the OLE Phase.

- Any TEAE
- Any treatment-related TEAE
- Any severe TEAE
- Any treatment-related severe TEAE
- Any serious TEAE
- Any treatment-related serious TEAE
- Any TEAE leading to study discontinuation
- Any TEAE leading to discontinuation of investigational product (IP)
- Any TEAE leading to discontinuation of IP and leading to study discontinuation
- Any TEAE leading to interruption of IP
- Any TEAE leading to death

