For patients who opt to continue in the OLE Phase of the study, only AEs starting strictly before the first dose in the OLE Phase will be summarized for the Double-Blind Treatment Phase, and any AEs that started on or after the first dose of treatment in the OLE Phase and up to 30 days after the last dose of treatment in the Double-Blind Treatment Phase will be included in a separate listing (for the OLE Phase reporting); these AEs will be included in the OLE Phase summaries. A listing of all the AEs that were ongoing (i.e. that are ongoing or have a stop date after the first dose of treatment in the OLE Phase) at the end of the Double-Blind Treatment Phase will be included in the OLE Phase reporting to capture additional information for those AEs (such as end date and potential treatments) and patients will not necessarily be on the same treatment as what they were randomized to in the Double-Blind Treatment Phase.

For the OLE Phase, the same data summaries and listings will be produced. The data will be tabulated for overall and by period

. Calculations for AE start and stop dates are detailed in Appendix 5.

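### The SAP's onset-only phase rule leaves AEs that worsen in the open-label extension out of the OLE adverse-event tables, and does not say which phase owns the later grade

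*SAP*

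**What the plan says.** SAP 9.6 puts both phases in one place: "The data collected for the Double-Blind Treatment Phase and the OLE Phase are included in the same database". A data cut-off is applied for the double-blind report. For the AEs of patients who go on to the OLE, that cut-off is spelled out only by start date: "any AE or medication that started up to and excluding the first dose of study drug in the OLE Phase". The OLE report has no cut-off, and its AE scope is "AE and concomitant medications started on or after the 1st dose of OLE study drug intake".

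SAP 12.6.1 repeats the split by onset. Its general definition of a treatment-emergent AE (TEAE) has two limbs: new events, and "any event already present that worsens in intensity or frequency after exposure and up to 30 days after the last dose of study drug". Protocol 9.4.3 also has both limbs. The OLE then gets its own sentence: "For the OLE Phase, any AE starting on or after the first dose of OLE treatment will be considered treatment emergent".

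Events still open when the double-blind phase ends are listed, not tabulated. "A listing of all the AEs that were ongoing" at that point goes into the OLE report to pick up later details. The SAP remarks there that these patients may no longer be on their randomized treatment.

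**The concern.** The TEAE tables in SAP 12.6.1 depend on attributes that can change after onset: maximum severity, seriousness, relatedness, and whether drug was stopped. A rule that looks only at the start date does not say which treatment period owns such a change.

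The case that matters is a patient whose event begins mildly under blinded treatment, who moves to open-label pitolisant, and whose event then becomes severe or serious or leads to withdrawal. That outcome belongs to the OLE period. If the OLE tables cannot count it, they understate worsening on long-term pitolisant. If the double-blind tables pick it up, an OLE-period outcome is credited to the randomized arm, which may be placebo.

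**Working it through.** The plan states no figure on this point, so there is none to reproduce. The check is a reading of the rules followed by simple arithmetic.

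**1. Can a record change after OLE entry?** Yes. Protocol 8.3.2 has ongoing AEs reviewed at each later contact, protocol 8.2.2 lets the investigator revise causality, and protocol 8.4.1 requires SAE reports to be updated. There is also time for it. Under protocol 9.5 and SAP 12.4.1 the double-blind results wait until every patient has finished or left that phase, while OLE entrants start open-label drug the day after Visit 5 (protocol 3.1.4).

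**2. Do the OLE rules have a place for worsening?** SAP 9.6 and the OLE sentence in SAP 12.6.1 both select on start date. Neither mentions worsening. SAP 6.1 does not list this as a change from the protocol.

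**3. Where does a worsening after OLE entry land?** Two facts are not stated: whether the site updates the old record or opens a new one, and whether the double-blind cut-off fixes attributes as well as selecting events.

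| Data entry | Cut-off fixes attributes? | Double-blind tables | OLE AE tables |
|---|---|---|---|
| New record, new start date | either | unaffected | counted |
| Same record updated | yes | grade as at OLE entry | not counted |
| Same record updated | no | later grade, under the randomized arm | not counted |

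The OLE omission occurs in both same-record rows. The transfer to the randomized arm occurs only in the last.

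**4. Size of one event.** Protocol 9.2 plans 20 patients per arm, and SAP 12.6.1 counts a patient once per row.
- Double-blind, single arm: 1/20 = 5 percentage points; two patients 2/20 = 10; three 3/20 = 15.
- Double-blind, pooled pitolisant: 1/40 = 2.5 points.
- OLE: one missed patient is 1/n, where n is the number treated in the OLE. The documents do not give n. Assuming all 60 enter, 1/60 = 1.7 points; assuming half enter, 1/30 = 3.3 points.

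These are shifts in the severity, seriousness, relatedness or discontinuation rows. The double-blind row for any TEAE does not move, because the event is already in it. A row also stays put if the patient is already counted there for another event.

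**The case against.** **The cut-off may already do the job.** SAP 9.6 says only data related to the double-blind phase are reported, and the stated purpose of the ongoing-AE listing suggests that later information is meant for the OLE report. That is a fair reading, but it is not written as a rule for attributes. If it is right, the worsening is counted in neither phase's AE tables.

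**Worsening may be its own AE.** Protocol 8.1.1 gives exacerbation of a pre-existing condition as an example of an AE. Protocol 6.5.6 asks for worsening seizures (in patients with a seizure history) and worsening anxiety to be recorded as AEs. Where sites open a new record, the OLE tables work. No document says this is the practice for every AE. The OLE sentence in SAP 12.6.1 could also be read as adding to the general definition, but the OLE scope in SAP 9.6 remains limited to new onsets. Table shells are in a separate document and might settle the matter.

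**Three stronger inferences are not supported.**
- A reader might infer that such an event is counted nowhere in the OLE. SAP 12.1.1 tabulates patients who stop OLE drug, by reason; SAP 12.3.2.2 counts dose adjustments due to AEs; and the listing shows the event itself.
- A reader might infer that the error runs against placebo. The same rule applies to both pitolisant arms, so their counts could be inflated too.
- A reader might infer biased follow-up, because for patients who decline the OLE "all AEs and medications reported through the final 30-day safety follow-up telephone contact will be reported as part of the Double-Blind Treatment Phase" while entrants stop at their first OLE dose. Entrants cannot have drug-free follow-up, the 30-day window is the protocol's own TEAE definition (9.4.3), and bias between arms needs OLE uptake to differ by arm, which is not given. The sign is not fixed either: a patient stopping on Day 40 would have 40 + 30 = 70 days, fewer than the 77 of a completer who enters.

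**Conclusion.** The point holds as a gap in the OLE counting rule. A double-blind-onset AE that worsens, turns serious or ends open-label pitolisant on the same record is absent from the OLE TEAE, serious-TEAE and discontinuation-TEAE tables, although the TEAE definitions in both documents include worsening. This rests on one assumption, that at least some sites update the existing record.

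That the later grade also enters the double-blind table under the randomized arm is a possibility left open by silence, not something the SAP prescribes. It needs the further assumption that the cut-off does not fix attributes. If so, each affected patient can move a row by 5 points in a 20-patient arm. Nothing in the documents allows an estimate of how many patients would be affected. Safety is descriptive only, so no test is at stake; what is at stake is the correct period for a small number of important events.

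**What to change.** In SAP 9.6 and 12.6.1, add two sentences in substance:

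1. For AEs open at the first OLE dose, the double-blind tables use severity, seriousness, relatedness and action taken as of that date.
2. Any later worsening, change to serious, or withdrawal of drug for such an AE counts as an OLE treatment-emergent event, dated from the change.

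The AE completion instructions should say whether worsening opens a new record, so that the same event is not counted twice.

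The cost is SAP wording, programming, and a check of AE records open at OLE entry. Protocol 1.3.2 describes the double-blind phase as completed, so for that phase the work is a comparison of those records with the tables produced. The counting rule can still be applied in the separate OLE report planned in SAP 9.6. Because SAP 6.0 has the SAP approved before unblinding, a change made now should be dated and labelled accordingly.

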4.1.1. Inclusion Criteria

Each patient must meet all of the following criteria to be enrolled in this study:

- 1. Is able to provide voluntary, written informed consent (patient or parent[s]/legal guardian[s]) and, where applicable, voluntary, written assent (patient, as appropriate).
- 2. Has a diagnosis of PWS confirmed by genetic testing and patient medical records. Genetic testing will be provided by the Sponsor, if not confirmed based on the review of the patient's medical records.
- 3. Male or female patients ages 6 to 65 years at the time of enrollment.
- 4. Demonstrates adequate sleep duration via patient sleep diary during Screening defined as at least 8 hours of sleep per night for patients ages 6 to <12 years, at least 7 hours for patients ages 12 to <18 years, or at least 6 hours for patients ages ≥18 years, based on the mean number of hours from up to 14 nights (at least 7 nights must be recorded for evaluation).
- 5. Has EDS as determined by ESS-CHAD (parent/caregiver version) score \geq 12.
- 6. If taking hormone treatments (including growth hormone, testosterone, and estrogen supplements) and/or allowed chronic concomitant medication or supplements, patient must be on a stable dose of these medications for 3 months prior to randomization and for the duration of the Double-Blind Treatment Phase of the study; 10% variability in hormone dose is allowed.
- 7. If taking a wake-promoting treatment that could affect EDS (including stimulants, modafinil, and armodafinil), must be on a stable dose for at least 28 days prior to Screening and remain on a stable dose during the Double-Blind Treatment Phase of the study (dose adjustments will be permitted in the OLE Phase) or agree to wash out of treatment for 5 half-lives or 14 days, whichever is longer.
- 8. If taking a chronically administered sedating medication for management of behavioral manifestations (e.g., hypnotics, benzodiazepines, antipsychotics, alpha agonists, anticholinergics, and antidepressants) must be on a stable dose for at least 28 days prior to Screening and remain on a stable dose during the Double-Blind Treatment Phase of the study (dose adjustments will be permitted in the OLE Phase) or agree to wash out of treatment for 5 half-lives or 14 days, whichever is longer.

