12.3 Treatments

12.3.1 Prior, Concomitant and Prohibited Medications

Medications that stop prior to the first dose of study drug will be classified as prior medications. Medications that start on or after the first dose of study drug will be classified as concomitant. If a medication starts before the first dose of study drug and stops on or after the first dose of study drug (or is ongoing), then the medication will be classified as both prior and concomitant.

Medications will be categorized by medication group and subgroup according to World Health Organization (WHO) drug dictionary (the version used will be included in the tables and listings footnotes).

Missing or partial medication start/stop date will be imputed as described in Appendix 2. A conservative approach will be used when flagging medications.

Prior and concomitant medications will be summarized by preferred name and medication class. Frequency count and percentage of patients using each medication along with the number and percentage of patients using at least one medication within each medication and medication class will be presented. All medications will be listed.

For patients who opt to continue in the OLE Phase of the study, only medications starting strictly before the first dose in the OLE Phase will be summarized for the Double-Blind Treatment Phase, and any medications that started on or after the first dose of treatment in the OLE Phase and up to 30 days after the last dose of treatment in the Double-Blind Treatment Phase will be included in a

separate listing (for the OLE Phase reporting); these medications will be included in the OLE Phase summaries.

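### The OLE concomitant-medication summaries select drugs by start date, so drugs carried into the OLE are left out and long-term co-medication is understated

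*SAP*

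**What the plan says.** SAP 9.6 sets the scope of the OLE report. No data cut-off is applied to the datasets, but "only data related to the OLE Phase will be reported, i.e" introduces a list of what is included. The medication entry in that list is "AE and concomitant medications started on or after the 1st dose of OLE study drug intake".

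SAP 12.3.1 is consistent with this. For patients who continue into the OLE, "only medications starting strictly before the first dose in the OLE Phase will be summarized for the Double-Blind Treatment Phase". On the other side of the line, it takes "any medications that started on or after the first dose of treatment in the OLE Phase" (and within 30 days of the last double-blind dose), puts them in a separate listing, and adds that "these medications will be included in the OLE Phase summaries". The same section has a general rule for a drug that begins before the first dose of study drug and continues past it: "then the medication will be classified as both prior and concomitant". It also says, without naming a phase or report, that all medications will be listed.

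For adverse events, SAP 12.6.1 makes the same split by start date, then adds one item to the OLE report: "A listing of all the AEs that were ongoing" at the end of the double-blind phase.

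On background treatment, Protocol 4.1.1 admits patients on a wake-promoting drug (criterion 7) or a chronic sedating drug (criterion 8) if they "remain on a stable dose during the Double-Blind Treatment Phase of the study (dose adjustments will be permitted in the OLE Phase"). Criterion 9 has a similar provision for cannabidiol and tetrahydrocannabinol.

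**The concern.** A concomitant medication in the OLE is, in ordinary use, a drug taken while the patient receives open-label pitolisant. The SAP's criterion is instead whether the drug was *started* in that period. A patient who enters the OLE on a long-standing stimulant, antipsychotic or cannabidiol product and keeps taking it contributes nothing to the OLE medication summary for that drug.

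What is at stake is the description of long-term treatment. The OLE is one uncontrolled group reported in its own clinical study report (SAP 9.6, 12.4.2). A reader of that report needs to know what else the patients were taking, both to judge safety co-exposure and to know the setting in which effectiveness was observed. A summary holding only newly started drugs does not give this.

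**Working it through.** The plan states no figure on this point, so the check applies its rules to each kind of medication record.

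**Inputs**
- OLE inclusion rule: start date on or after the first OLE dose (SAP 9.6).
- Double-blind rule for patients who continue: start date strictly before the first OLE dose (SAP 12.3.1).
- Anchor for the first dose: SAP 9.2 defines the first dose date as the start of the double-blind phase. SAP 12.3.1 names the OLE explicitly when it means the first OLE dose.

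**Result by type of record**

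| Record | Taken during OLE? | Double-blind summary | OLE summary |
|---|---|---|---|
| (a) Started before the double-blind phase, ongoing in the OLE | Yes | Yes | **No** |
| (b) Started during the double-blind phase, ongoing in the OLE | Yes | Yes | **No** |
| (c) Started on or after the first OLE dose | Yes | No | Yes |
| (d) Stopped before the first OLE dose | No | Yes | No |

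Rows (c) and (d) are right. Rows (a) and (b) are drugs in use during the OLE that the OLE summaries omit.

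**Does the rule for drugs that are both prior and concomitant repair this?** No. It is tied to the first dose of study drug, which is the first double-blind dose. It makes a row (a) drug concomitant for the study, but SAP 9.6 then keeps only drugs that started in the OLE.

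**Who is affected?** Any drug held stable under criteria 7 to 9 was in use before the OLE began, so its original record falls in row (a). A drug whose dose changes in the OLE is less certain. Protocol 5.7 says changes go into the eCRF but not whether a change opens a new record with a new start date. If it does, the changed drug appears in the OLE summary while an unchanged one does not.

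**Size.** For a given drug class, let *N* be the number of OLE patients, *S* the number with at least one record started in the OLE, and *C* the number with carried-in use only. The summary shows *S/N*; actual use is *(S + C)/N*; the shortfall is *C/N*. The documents give no value for *C*.

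**The case against.** Four points can be made for the plan as it stands.

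- *The drugs are still reported.* This stands. They are in the double-blind summaries, the OLE datasets have no cut-off, and the SAP says all medications are listed. A reader might infer that the information disappears from the study; the documents do not support that. But the double-blind summary belongs to a different report, covers patients who may never have entered the OLE, and does not show which drugs continued. The listing provision is not tied to the OLE report, and a listing is not a summary.
- *Effectiveness is not distorted.* This also stands. A reader might infer that the OLE change scores are biased. They are changes from the pre-double-blind baseline (SAP 9.3, 12.4.2), so a drug taken unchanged throughout is present at both ends and explains little of the change. New starts could matter more, and the rule does capture those.
- *The adverse-event precedent is only a listing.* True: ongoing events are also kept out of the OLE summaries. However, an event that began earlier is not treatment-emergent in the OLE, whereas a drug still being taken is concomitant treatment there. The precedent shows that the SAP recognised carry-over for events and made no counterpart for medications.
- *The table shells are in a separate document* (SAP 12.0) and might show carried-in drugs. That is possible, but shells should follow the SAP, and the SAP wording excludes them. SAP 12.3.1 alone does not expressly bar these drugs; the exclusion comes from the restrictive wording of SAP 9.6.

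**Conclusion.** The concern holds for the OLE concomitant-medication summaries. As written, they omit every drug started before the first OLE dose and still in use, and so understate co-medication during long-term treatment. This follows from the selection rule whatever the level of background use; how many patients it touches is not known from the documents.

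The conclusion rests on reading the list in SAP 9.6 as complete, and on continued drugs keeping their original start date in the database. It is a descriptive reporting defect in an uncontrolled extension. It leaves the double-blind results and the OLE effectiveness estimates unchanged, and does not call for an additional effectiveness analysis.

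**What to change.** In SAP 9.6 (OLE part) and 12.3.1, define an OLE concomitant medication as any medication started on or after the first OLE dose, or ongoing at that dose. Show the two kinds separately, flagged *ongoing at OLE entry* and *started in OLE*, as the medication counterpart to the carry-over listing for adverse events in SAP 12.6.1. State how a dose change to a carried-in drug is classified, so that it does not appear as a new start.

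No new data are needed. Protocol 5.7 has start dates and changes recorded, and SAP Appendix 2 already handles stop dates and ongoing status. The cost is a few lines of SAP text, some programming and slightly longer tables. SAP 6.0 ties the plan to protocol Amendment 5 and allows for updates after later protocol changes, so this could be made in any revision that takes account of Amendment 6.
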